## 5) Statistical Considerations

[name] and [name], PhD will be responsible for the Bioinformatics analysis, while [name] will be responsible for statistical analysis of the predictive model during the training stage (Objective 1). The ECOG Statistical Center will be responsible for the independent validation in Objective 2.

**Endpoints (outcomes):** The primary objective of this project is to develop and then independently validate a predictive model to distinguish between HPV-mediated HNSCC patients who may receive de-intensified treatment versus patients who should undergo more intensive treatment, including trans-oral robotic surgery. All participants in ECOG 3311 underwent such surgery, and then were classified into three strata; patients from the intermediate-risk strata were then randomized to two levels on de-intensification. These populations are represented by Arm D of ECOG 3311, versus Arms A-C. While the development of the model will be primarily the responsibility of the bioinformatics component at the University of Pittsburgh, the statistical validation of the model, including the estimation of the area under the receiver operating curve (AUC) using an independent validation set, will be responsibility of the ECOG Statistical Center.

**Case selection:** For training, 100 cases from ECOG 3311 Arms A+B+C are requested; the University of Pittsburgh will supply 100 cases similar to those from ECOG 3311 Arm D. For validation, 70 cases from ECOG 3311 Arms A+B+C and 70 cases from Arm D are requested. We will request up to 90 cases of each category to obtain at least 70 with sufficient material for DNA/RNA extraction and sequencing.

**Statistical analysis plan for addressing the primary objectives:** Please see **Section 9.f.d**, Informatics for Objective 1, for the plan for the development of the predictive model. The statistical analysis plan applies to Objective 2, independent validation of the predictive model, which is to be carried out by the ECOG Statistical Center. The 140 ECOG 3311 samples with sufficient material for sequencing will be assayed for somatic alterations and gene expression profiles in a similar fashion to the training set, and then submitted to the ECOG Statistical Center so that they can perform an independent validation of the trained model. They will generate an ROC curve and calculate the area under that curve with a 90% confidence interval to test the null hypothesis that  $AUC < 0.60$ .

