#### 5.1.8.4 Definition of Unknown-Risk Patient Cohort and Management: Arm C (5-7 weeks)

Patients found to have N2C or N3 disease on final pathologic analysis are at unknown risk for recurrence, but are not candidates for deintensified adjuvant therapy in this trial. These patients will be treated on Arm C.

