In the original design, the risk distribution was assumed to be 10% low risk, 60% intermediate risk, and 30% high risk, and an interim analysis for the first 59 patients who complete transoral resection was scheduled. Based on the analysis results, among the 104 evaluable patients (not ineligible based on current evaluation, and started treatment on step 2), the estimated risk distribution is: 8% low risk, 48% intermediate risk and 32% high risk (13 (12%) patients had potentially misclassified risk category/ arm based on their surgical data and the study team is taking various actions trying to improve this). As was stated in the original design, in case the proportion of the intermediate risk patients is off over 5% from the anticipated 60%, the accrual goal would be adjusted, With this new accrual goal, we expect at the end of the study ~180 evaluable patients would be intermediate risk, ~120 high risk, and ~30 low risk.

In analyzing the 2-year PFS rate, 90% exact binomial confidence intervals will be computed for each arm. Only eligible patients with confirmed P16+ status who started radiotherapy will be analyzed (by arm). The regimen will be considered worthy of further study if the higher limit of the computed 90% CI exceeds 85%.

Comparisons of 2-year PFS rates between Arms B and C, Arms B and D, and Arms C and D are exploratory endpoints. Since one of the randomized arms proposed in this study is likely to be selected for a follow-up phase III study, the exploratory comparison of 2-year PFS rate between the two randomized arms is more important and a p-value  $\leq 0.05$  will be considered statistically significant. For the other two comparisons (Arms B and D; Arms C and D), the Type I error rate of 5% will be divided by the two tests (i.e., 0.05/2 considered statistically significant). Therefore, the family-wise error rate of 0.10 will be protected for the multiple comparisons in the 2-year PFS rate among arms. Power for various differences in the 2-year PFS rate is shown below, assuming a two-sided Fisher's exact test and 90 analyzable patients in Arms B or C, and 120 analyzable patients in arm D.

Difference in 2-year PFS rate between arms	Arm C vs. Arm B	Arm B (or C) vs. Arm D
10% (85% vs. 75%)	0.32	0.27
15% (85% vs. 70%)	0.62	0.58
20% (85% vs. 65%)	0.85	0.83
25% (85% vs. 60%)	0.96	0.96

*Interim Analysis—1-year PFS rate*

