### Statistical justification for sample size

**Sample size estimate:** Objective 1: 100 samples from Arms A+B+C; the University of Pittsburgh will provide 100 samples similar to those of Arm D. Objective 2: 140 samples; 70 from Arm D and 70 from Arms A+B+C.

**Rationale for the sample size estimate:** Objective 1: Systematic determination of required sample sizes for training of predictive models has proven intractable, but, based on our previous experience and the preliminary work described in **Section 8.e**, 200 samples should be adequate for an effective classifier. Objective 2: The method presented in Pepe [17] (pp. 224-227) for determining the sample size for a test on AUC using binormal ROC curves was used, based on a one-sided null hypothesis test  $AUC < 0.6$  at  $\alpha = 0.05$  and 80% power. We used the binormal parameters  $a_0 = 0.36$  and  $b_0 = 1$  for the reference AUC (0.6) and  $a_1 = 0.81$  and  $b_1 = 1$  for the expected AUC (0.72). It was determined that we will achieve the stated power if the true  $AUC \geq 0.75$  on independent samples, which we believe is achievable based on our preliminary analysis, where we observed  $AUC > 0.9$  on the training set.

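### Appendix X validates the biomarker classifier against assigned arm, without correcting possible arm/pathology mismatches; errors across the Arm D boundary would lower the AUC and may take power below the stated 80%

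*Combined protocol and SAP*

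**What the plan says.** Appendix X, 5) Statistical Considerations, sets up two populations, patients suited to de-intensified treatment and patients who need more, and identifies them by arm: "These populations are represented by Arm D of ECOG 3311, versus Arms A-C". The validation sample is fixed in the same terms: "Objective 2: 140 samples; 70 from Arm D and 70 from Arms A+B+C". The test is a "one-sided null hypothesis test" of AUC below 0.6 "at $\alpha = 0.05$ and 80% power". The calculation uses a0 = 0.36, b0 = 1 "for the reference AUC (0.6") and a1 = 0.81, b1 = 1 "for the expected AUC (0.72"). The next sentence says that the stated power holds if the true AUC is at least 0.75. The decision tool is a 90% confidence interval for the AUC.

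The main protocol, Section 9.3, reports on 104 evaluable patients at the interim look: 8% low, 48% intermediate and 32% high risk, and "13 (12%) patients had potentially misclassified risk category/ arm based on their surgical data". It adds that the team was acting to improve this.

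Section 3.2.2 makes patients who are not placed in the right risk category ineligible. Section 12.1 uses retrospective central review to decide evaluability. Appendix X, 3) Biospecimen Requirements, requests all 266 cases with samples. Neither that section nor the case-selection paragraph limits cases to eligible or centrally confirmed patients, or says how a known mismatch is handled.

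**The concern.** Appendix X states its aim in biological terms: sections 1 and 2 speak of an aggressive tumour phenotype and of the pathologic features that send a patient to Arm D. Arm is a stand-in for those features. Where a site put a patient in an arm that the pathology does not support, a good genomic model should disagree with the arm, and the analysis would count that as a model error. The reported AUC would then understate accuracy against pathology, and a model that meets its target could fail the AUC test. The pathology that defines the class is already collected.

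**Working it through.** **Inputs.** 70 versus 70 cases, one-sided 5%, null AUC 0.60, design AUC 0.72 (a1 = 0.81) and also 0.75, all from Appendix X. Mismatch 13/104 = 12.5% (printed as 12%), from Section 9.3. The percentages there, 8 + 48 + 32 + 12, sum to 100, so the 13 appear to be set apart from the risk groups. That leaves about 58 low or intermediate (56% of 104) and 33 high risk (32% of 104).

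**The plan's own figure.** With b = 1, AUC = Φ(a/√2), so a1 = 0.81 gives Φ(0.573) = 0.7166. The Mann-Whitney standard error under binormal scores, 70 per group, is 0.0429 at 0.7166 and 0.0477 at 0.60. Power under three usual forms of the test:

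- Plain Wald: Φ((0.7166 − 0.60)/0.0429 − 1.645) = 0.858.
- Null variance in the critical value: Φ((0.7166 − 0.60 − 1.645 × 0.0477)/0.0429) = 0.813.
- Logit scale: 0.795.

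The last two reproduce the stated 80%. At exactly 0.72 the three give 82-88%. At 0.75 they give 94-98%, so the two design AUCs in Appendix X are not interchangeable.

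**Effect of label error.** Let p be the share of labelled Arm D cases that are truly not high risk, and q the share of labelled Arms A-C cases that truly are. If errors are unrelated to the score,

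AUC_obs = (1−p)(1−q)·AUC + pq·(1−AUC) + [p(1−q) + q(1−p)]·0.5 = 0.5 + (AUC − 0.5)(1 − p − q).

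**Scenarios.** The documents do not say how many of the 13 cross the D boundary, or in which direction, so these are assumptions. A proportional spread of all 13 gives p = q = 0.125. All 13 in A-C gives q = 13/(58+13) = 0.183. All 13 in D gives p = 13/(33+13) = 0.283.

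Example, half crossing, proportional: p = q = 0.0625, so AUC_obs = 0.5 + 0.22 × 0.875 = 0.6925, with SE 0.0442. Plain Wald power is Φ(0.0925/0.0442 − 1.645) = 0.67.

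| Of the 13, crossing the D boundary | p + q | True 0.72: AUC_obs, power | True 0.75: AUC_obs, power |
|---|---|---|---|
| None | 0 | 0.720, 82-88% | 0.750, 94-98% |
| A quarter, proportional | 0.063 | 0.706, 73-79% | 0.734, 89-94% |
| Half, proportional | 0.125 | 0.693, 62-67% | 0.719, 81-87% |
| All, in A-C | 0.183 | 0.680, 51-55% | 0.704, 71-77% |
| All, proportional | 0.250 | 0.665, 38-41% | 0.688, 58-63% |
| All, in D | 0.283 | 0.658, 33-35% | 0.679, 51-55% |

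Ranges cover the three test forms. Simulation with a DeLong 90% interval (6,000 runs) agrees for the all-proportional row: 42% at 0.72 and 61% at 0.75. Direction matters too. If half cross and all of those sit in D, p = 6.5/39.5 = 0.165 and power is 55-59% at 0.72 and 75-81% at 0.75.

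Power drops below 80% once p + q reaches about 0.015-0.055 if the true AUC is 0.72, and about 0.135-0.17 if it is 0.75.

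**The case against.** The strongest reply is that no power loss has been demonstrated. The 13 are potential misclassifications at an interim look, with correction under way. They span all categories, and an error between Arm A and Arms B/C leaves the D versus A-C label unchanged. At 0.75, the AUC to which Appendix X ties its power, there is room for appreciable error. Much of Appendix X also speaks of predicting arm stratification as such. If 0.72 or 0.75 already refers to the arm label, the attenuation is built in and subtracting it again would count it twice. Mislabelled cases may also be borderline in pathology and in score, which would lower the AUC less than the formula does. Sections 3.2.2 and 12.1 may remove some of these cases from the parent analysis. All of this stands, and it limits the claim about size. It does not remove the gap: Appendix X does not carry those safeguards over, so known mismatches can enter the AUC test.

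Three stronger readings are tempting, but the documents do not support them.

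- **That power is cut well below 80%.** This needs a boundary-crossing rate that the documents do not give, and in several scenarios at 0.75 it is false.
- **That arm is the label throughout training.** Only the Arms A+B+C half of the training set comes from the trial. The 100 high-risk training cases come from the University of Pittsburgh and are described only as similar to Arm D.
- **That N2c/N3 patients on Arm C are label errors.** Section 5.1.8.4 says they "are not candidates for deintensified adjuvant therapy in this trial. These patients will be treated on Arm C", which fits poorly with a class described as suitable for de-intensification. But the opening of Section 9 sends them to Arm C only if they lack the high-risk features, so by pathology they belong in the non-high-risk class. They do not enter the figures above.

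**Conclusion.** The concern holds as a weakness in the choice of reference label, with a possible but unquantified loss of power. Appendix X validates against an arm label that the trial itself found potentially wrong in one patient in eight, and it states no correction. The loss runs from none, if no errors cross the D boundary, to power of 33-55% (true AUC 0.72) or 51-77% (true AUC 0.75) if all 13 do. These figures assume that the interim rate carries over to the validation cases, that errors are unrelated to the score, and that the design AUC refers to true pathology. The case for change rests less on any one power figure than on a better label being available from data already collected.

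**What to change.** In Appendix X, define the reference class of the trial cases, in training and validation, by recorded surgical pathology using the definition in Section 3.2.2: positive margin, ECE greater than 1 mm, or 5 or more positive nodes is high risk; otherwise not.

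- Take the class after the study team's reconciliation or central review, and lock it before sequencing results are seen. Section 12.1 lists ECE but not margins or node counts, so those come from the surgical pathology data submitted under Section 11.2.1.
- Relabel mismatched cases where the pathology settles the class. Exclude only those it cannot settle.
- Report assigned arm as a sensitivity label.
- Keep N2c/N3 patients without high-risk features in the non-high-risk class, with their exclusion at most a sensitivity analysis.
- State one design AUC and say which label it refers to.

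The cost is wording and data already held. A few cases would be relabelled or dropped. Slack is limited: 100 + 70 + 70 = 240 trial cases are needed of 266 available, which is why relabelling is preferable to exclusion.

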- Excision repair cross-complementation group 1 (ERCC1) is a rate-limiting enzyme in the nucleotide excision repair pathway that removes cisplatin-induced DNA adducts (24,25). Recent studies have shown that ERCC1 SNP (Thr259Thr) and high ERCC1 protein expression in tumors are associated with poor survival in HNSCC (26-28). When patients with stage I or II were treated with radiation therapy alone, the patients with ERCC1 SNP resulting in Thr259Thr (4.1%) compared to Thr259Lys (25.5%) or Lys259Lys (70.4%) had shorter time to progression (11.6 vs. 87.6 or 85.2 months) and median survival (27.9 vs. 89.9 or 88.3 months) (28). Furthermore, low ERCC1 protein expression in the tumors was seen in 27-29% of the patients and associated with higher response rate and lower risk of death when the patients were treated with cisplatin-based induction chemotherapy or cisplatin-based concurrent CRT (26,27). Therefore, we hypothesize that the patients with ERCC1 SNP Thr259Thr will have shorter time to progression and survival compared to the patients with Thr259Lys or Lys259Lys because of radiation resistance associated with Thr259Thr. We also hypothesize that the patients with lower expression of ERCC1 protein in their tumors will have higher response to cisplatin-based chemoradiotherapy, and longer time to progression and survival.
- 1.6.4      Correlation of radiologic markers with pathologic nodal status
- Preoperative CT/MRI scans will be analyzed for nodal stage and prediction of ECE, and correlated with final pathologic nodal stage, presence and extent of ECE (< or >1mm).
- 1.6.5      HPV DNA measurement and alteration in serum and saliva
- HPV DNA and seropositivity to HPV antigens will also be measured quantitatively and qualitatively, before and after surgical and adjuvant treatment to measure stability and predictive ability over time in a prospective treated population. Baseline and posttreatment cytokines are potentially predictive of outcome. Furthermore, the association between serologic markers (detected in blood at baseline and two other timepoints, including cytokines, chemokines, growth factors, and angiogenic factors in blood and treatment efficacy will also be examined.
- DNA from buffy coat or PBMCs will be analyzed for quantitative and qualitative alterations in HPV DNA. These analyses will be performed under the direction of [name], PhD.
- 1.6.6      Oral or serum HPV DNA level may correlate with PFS

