#### 3.1 Registration to Surgery (Arm S)

\_\_\_\_\_ 3.1.1 Age  $\geq$  18 years.

\_\_\_\_\_ 3.1.2 ECOG performance status of 0 or 1.

Rev. 2/15

\_\_\_\_\_ 3.1.3 Patients must register to Step 1 prior to surgery.

\_\_\_\_\_ 3.1.4 Patients must have newly diagnosed, histologically or cytologically confirmed squamous cell carcinoma or undifferentiated carcinoma of the oropharynx. Patients must have been determined to have resectable oropharyngeal disease. Patients with primary tumor or nodal metastasis fixed to the carotid artery, skull base or cervical spine are not eligible

Rev. 2/15  
Rev. 9/16

\_\_\_\_\_ 3.1.5 Patients must have AJCC TNM tumor stage III, IV a, or IV b (with no evidence of distant metastases) as determined by imaging studies (performed  $<$  30 days prior to registration) and complete neck exam, from the skull base to the clavicles. The following imaging is required: CT scan with IV contrast or MRI.

AJCC TNM tumor stage III, IV a, or IV b?

Stage \_\_\_\_\_ Date scans performed \_\_\_\_\_

CT scan with IV contrast or MRI?

The primary tumor should be cT1 or T2 and cervical nodes cN1, N2a, or N2b based on clinical or radiographic criteria.

Rev. 6/14  
Rev. 2/15

\_\_\_\_\_ 3.1.6 Patients must have biopsy-proven p16+ oropharynx cancer; the histologic evidence of invasive squamous cell carcinoma may have been obtained from the primary tumor or metastatic lymph node. It is required that patients have a positive p16 IHC (as surrogate for HPV) status from either the primary tumor or metastatic lymph node.

\_\_\_\_ 3.1.7 Carcinoma of the oropharynx associated with HPV as determined by p16 protein expression using immunohistochemistry (IHC) performed by a CLIA approved laboratory. Using p16 antibody obtained from Roche mtm laboratories AG (CINtec, clone E6H4) is recommended.

Confirmed p16+ disease? Yes \_\_\_\_\_ No \_\_\_\_\_

\_\_\_\_ 3.1.8 No prior radiation above the clavicles.

\_\_\_\_ 3.1.9 Patients with a history of a curatively treated malignancy must be disease-free for at least two years except for carcinoma in situ of cervix, melanoma in-situ (if fully resected), and/or non-melanomatous skin cancer.

History of curatively treated malignancy?

Yes \_\_\_\_\_ No \_\_\_\_\_

If yes, disease-free for at least two years?

Yes \_\_\_\_\_ No \_\_\_\_\_

Rev. 1/16

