## 1) Objectives

The primary objective is to identify genomic biomarkers in HPV-mediated HNSCC that predict an aggressive tumor phenotype and, thus, patients who should not undergo treatment de-intensification with trans-oral robotic surgery (TORS).

- a. **Objectives:** 1) Develop a predictive model that, using Whole Exome Sequencing and RNA-Seq, predicts risk stratification and clinical outcome after observation, radiation alone, or chemoradiation. Generate a rich genomic and transcriptomic dataset for a novel, rapidly increasing subset of H&N cancers to provide collaborative opportunities for translational research to understand this newly emerging cancer. 2) In an independent set of samples from ECOG 3311, test the one-side null hypothesis that the AUC of the ROC curve of the predictive model is less than 0.6 at  $\alpha=0.05$ . This test is to be performed by the ECOG Statistical Center to ensure independence of the validation from the training.
- b. **Hypotheses:** 1) A predictive model that can be used to predict patients with HPV-mediated who are candidates for de-intensification can be developed using Whole Exome Sequencing and RNA-Seq. 2) In an independent validation set, it can be demonstrated that the AUC of the ROC curve of this predictive model is greater than 0.6.

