Preliminary evaluation of ECOG 3311 arm stratification has shown that ~30% of patients enrolled were stratified into arm D (tri-modality therapy), based on adverse pathologic risk factors. Tri-modality therapy is well established to have a more severe side effect profile, compared to surgery alone and surgery with adjuvant radiation, particularly, in regards to swallowing. Thus, identification of patients with biologically more aggressive cancers prior to treatment decision-making is vital for avoiding tri-modality therapy, if not absolutely necessary. All patients enrolled in ECOG 3311 have cT1 or T2 and cN1, N2a, or N2b disease, based on clinical or radiographic criteria, and are thus indistinguishable pre-operatively. At this time, no biomarkers exist that predict a more aggressive tumor phenotype or clinical pathologic features that would necessitate stratification into arm D of ECOG 3311 and, thus, tri-modality therapy. ECOG 3311 presents a unique opportunity to investigate such biomarkers in a cohort of HPV+ OPSCC patients with tightly annotated clinical and pathologic data. Of note, [name] is the PI, the highest accruing surgeon nationally to E3311, and personally funded the preliminary genomic/transcriptomic analysis and characterization, using UPMC specimens, to provide feasibility for the proposed studies using additional specimens from this trial.

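### Appendix X validates the genomic score only against a fixed AUC of 0.60, so a positive result cannot show that it adds anything to pre-operative staging

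*Combined protocol and SAP*

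**What the plan says.** Appendix X, 1) Objectives, sets two tasks: build a model from whole exome sequencing and RNA-Seq, then, in independent trial samples, "test the one-side null hypothesis that the AUC of the ROC curve of the predictive model is less than 0.6 at" the one-sided 5% level. Section 5) Statistical Considerations makes this operational: "They will generate an ROC curve and calculate the area under that curve with a 90% confidence interval to test the null hypothesis that" AUC is below 0.60. The validation set is 70 cases from Arm D and 70 from Arms A, B and C together. The appendix gives no reason for choosing 0.60. It specifies no clinical or imaging comparator, adjustment, matching on clinical nodal stage or added-value test.

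The purpose is in section 2) Background and Rationale: to find, before surgery, the patients who would end in Arm D, so that alternatives can be considered. That section says all enrolled patients are cT1 or T2 and cN1, N2a or N2b, "and are thus indistinguishable pre-operatively".

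Other parts of the protocol bear on that statement:
- Section 3.1.5: "The primary tumor should be cT1 or T2 and cervical nodes cN1, N2a, or N2b based on clinical or radiographic criteria".
- Section 3.2.2: high risk (Arm D) means a positive margin, ECE above 1 mm, or five or more metastatic nodes.
- Section 1.6.4: "Preoperative CT/MRI scans will be analyzed for nodal stage and prediction of ECE", to be correlated with pathologic nodal stage and with the presence and extent of ECE. Section 12.1 repeats this plan.

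**The concern.** The classification target is a pathologic risk group, and two of its three defining features are nodal. Clinical nodal stage and imaging signs of ECE are therefore natural candidate predictors, known before surgery. A gene-expression score could follow nodal burden, clear 0.60, and carry no information that the work-up does not already hold.

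The background statement does not remove this worry. Sharing one eligibility range is not the same as being alike within it: cT1 against T2, and cN1 against N2a against N2b, are observable differences. The protocol's own plan to predict ECE from imaging treats pre-operative findings as possibly informative.

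At stake is the step from a positive test to a claim that the score can select patients before surgery. That step needs added value, and the plan does not test for it.

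**Working it through.** **1. The plan's power figure.** Inputs (Appendix X, Statistical justification for sample size): null AUC 0.60; binormal a1 = 0.81, b1 = 1; one-sided alpha 0.05; 70 v 70; stated power 80%.

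Binormal AUC = Φ(a/√(1+b²)). For a0 = 0.36 this is Φ(0.255) = 0.600. For a1 = 0.81 it is Φ(0.573) = 0.717.

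Hanley-McNeil standard errors with 70 v 70 are 0.0478 at 0.60 and 0.0432 at 0.717. Power = Φ[(0.1166 − 1.645 × 0.0478)/0.0432] = Φ(0.88) = 0.81.

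The 80% is reproduced, at an AUC of 0.72. The same section attaches it to a true AUC of at least 0.75, where power is about 0.96. That mismatch is separate and should be reconciled.

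**2. The bar in practice.** With a standard error of 0.045 near the boundary, the lower 90% limit exceeds 0.60 once the observed AUC reaches about 0.60 + 1.645 × 0.045 = 0.674, or roughly 0.675.

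**3. How often a score with no new information passes.** The documents give no AUC for clinical stage or imaging ECE and no table of clinical nodal stage by arm. The clinical AUC is therefore an assumption, taken from 0.55 to 0.75. The clinical variable is binormal, and the rule is a DeLong lower 90% limit above 0.60 with 70 v 70. The proxy is 0.8 × clinical value + 0.6 × independent noise, so its true AUC is Φ(0.8 × Φ⁻¹(clinical AUC)). There were 20,000 simulated data sets per setting.

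| Assumed clinical AUC | Pure restatement passes | Proxy's true AUC | Proxy passes |
|---|---|---|---|
| 0.55 | 0.004 | 0.54 | 0.003 |
| 0.60 | 0.05 | 0.58 | 0.02 |
| 0.65 | 0.30 | 0.62 | 0.13 |
| 0.70 | 0.72 | 0.66 | 0.40 |
| 0.75 | 0.96 | 0.71 | 0.76 |

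Smaller separate simulations differ by about 0.02 (for example 0.28 in place of 0.30, and 0.74 in place of 0.76). With a correlation of 0.5 the proxy passes with probability 0.02, 0.07 and 0.19 at clinical AUCs of 0.65, 0.70 and 0.75.

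**4. A yes/no clinical variable.** Its AUC = 0.5 + (difference in prevalence)/2. If cN2b were present in 65% or 70% of Arm D and 50% of Arms A-C, the AUC is 0.575 or 0.60, and the variable itself passes with probability 0.01 or 0.05. At 80% v 50% (AUC 0.65) it passes with probability 0.39. No document supports one split over another.

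**5. Which added-value test suits 70 v 70.** Take a genomic AUC of 0.72, a clinical AUC of 0.65 (assumed), and within-arm correlations of 0, 0.3 and 0.6.
- Paired AUC difference (0.72 − 0.65 = 0.07; SD about 0.062, 0.053 and 0.040), one-sided 0.05: power 0.30, 0.37 and 0.52.
- Likelihood-ratio test of the genomic score added to a logistic model with the clinical variable, one-sided 0.05: power above 0.99, 0.99 and 0.97.

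For the pure proxy (correlation 0.8, no new information), the likelihood-ratio test passes 0.047 to 0.055 of the time at clinical AUCs of 0.65 to 0.75, which is its nominal level.

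**The case against.** The strongest reply is that the planned test does exactly what it says. The stated hypothesis is AUC > 0.60; nothing in Appendix X claims superiority to staging, and the test is valid for discrimination. This stands. A reader might infer that the validation test is wrong or that its own conclusion fails. It does not. The gap lies between that conclusion and the wider aim of pre-operative selection.

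A reader might also infer that 0.60 was chosen because patients were thought alike before surgery. The documents do not say so: the phrase is in the background, and 0.60 is set elsewhere without a reason.

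A third tempting reading is that clinical stage is shown to predict Arm D well. It is not. Planning to correlate imaging with pathology is no evidence that imaging predicts. Eligibility narrows the clinical spread (cT1-T2, cN1-N2b, no matted or fixed nodes under section 3.1.11). Multiple ipsilateral nodes straddle the arms, since two to four count as intermediate risk and five or more as high risk. The positive-margin route to Arm D is known only after surgery. The clinical AUC may therefore be modest, and the risk of a misleading pass small. This too stands, and is why the size is given as a range that includes values near zero.

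None of it supplies the missing comparison. Whatever the clinical AUC is, the planned test cannot separate new genomic information from stage.

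**Conclusion.** The point holds in a limited form. A positive result would support AUC > 0.60, but not a claim that the score improves on pre-operative staging, and the description of patients as alike before surgery does not match the protocol's own eligibility range and imaging plan.

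The absence of a comparator is read directly from the documents. The probability of being misled rests on the assumed clinical AUC, the binormal model and the assumed overlap between score and stage. It is a real risk from about 0.65 upwards and minor at 0.60 or below. This affects a correlative sub-study, not the trial's primary endpoint, so it is an improvement that should be made rather than a fatal flaw.

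**What to change.** Keep AUC > 0.60 as the primary validation test. Before the validation labels are used, add to Appendix X, section 5:

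- A pre-specified clinical comparator of cT and cN, with its coding fixed. Add radiologic ECE and smoking only where recorded. Sections 1.6.4 and 12.1 plan the imaging analysis without stating readers or criteria, and section 4.2.4.2 names smoking as a stratification factor for intermediate risk only, so availability in all arms needs checking.
- In the same 140 cases, the comparator's AUC with a 90% confidence interval.
- A one-sided 0.05 likelihood-ratio test of the locked genomic score in a logistic model that contains the clinical variables.
- The paired AUC difference with its interval as description only. As a gate it would reject a useful marker about half the time or more (power 0.30 to 0.52 above).
- A sentence limiting any claim of a pre-operative selection marker to the case where added value is shown.

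In section 2, replace the statement that patients cannot be told apart before surgery with wording that reflects the cT1-T2 and cN1-N2b range.

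The cost is a few lines and one extra analysis; cT and cN are set at registration and no new specimens are needed. Power for added value falls if the score overlaps heavily with stage, and the final claim may be weaker.
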